7.10. Generalizability

Whether a finding from a drug safety study in the US that a medication is associated with an adverse event (AE) is relevant for the EU population (and vice versa) is primarily a function of the internal and external validity of the study. For this reason, this study will use a rigorous set of epidemiologic design and analysis methods in an effort to estimate causal effects of *Duavee* with as much control as possible for various sources of error (eg, selection, misclassification, confounding). It follows that if a valid independent drug effect is found in this study, it would be relevant to the *Duavee* EU population. If a result is considered valid, then it is of interest to question to whom the result applies. Allowing that all populations differ from one another in one respect or another, Pfizer is focused upon whether women using *Duavee* in the US will differ from women using *Duavee* in the EU with regard to susceptibility to a particular adverse effect. Although indications for the drug are not identical between US and EU, it is expected that the populations would be largely similar in terms of their risks for these targeted safety endpoints. While the ethnic and racial distribution of postmenopausal women in the US and EU is certain to be different, there is no medical evidence to suggest these factors would modify the relative risk of these safety endpoints between *Duavee* and E+P HRT.

8. PROTECTION OF HUMAN SUBJECTS

8.1. Patient Information and Consent

There is no active enrollment or active follow-up of study subjects, and no data are collected directly from individuals. HealthCore maintains Data Sharing Agreements (DSAs) and

Business Associate Agreements with all covered entities who provide data to the HIRD. HealthCore's access, use, and disclosure of Protected Health Information (PHI) are in compliance with the Health Insurance Portability and Accountability Act (HIPAA) Privacy Rule [45 Code of Federal Regulations (CFR) Part 160 and Subparts A and E of Part 164]. HealthCore does not access, use, or disclose identifiable PHI unless under a specific waiver of authorization (e.g., a HIPAA Waiver of Authorization from an IRB). HealthCore accesses the data in a manner that complies with federal and state laws and regulations, including those related to the privacy and security of individually identifiable health information.

8.2. Patient Withdrawal

Not applicable.

8.3. Institutional Review Board (IRB)/Independent Ethics Committee (IEC)

The proposed study is designed as an analysis based on medical and pharmacy claims data from a large insured population in the US augmented with information obtained from medical records. Protected Health Information must be accessed from medical records in order to adjudicate the safety endpoints of endometrial hyperplasia and endometrial cancer. A HIPAA Waiver of Authorization will be applied for from an IRB prior to any PHI being identified. As the IRB is independent, HealthCore cannot control the approval or whether there are conditions for the approval. A copy of the IRB approval letter will be forwarded to Pfizer by HealthCore.

At no time during the conduct of this study will HealthCore provide to Pfizer information identifying patients or providers.

8.4. Ethical Conduct of the Study

This study will be conducted in accordance with applicable legal and regulatory requirements, as well as with scientific purpose, value and rigor and follow generally accepted research practices described in Guidelines for Good Pharmacoepidemiology Practices (GPP) issued by the International Society for Pharmacoepidemiology (ISPE), and the EMA, ENCePP Guide on Methodological Standards in Pharmacoepidemiology.

9. MANAGEMENT AND REPORTING OF ADVERSE EVENTS/ADVERSE REACTIONS

This study uses existing health care databases, in which it is generally not possible to link (ie, identify a potential association between) a particular product and medical event for any individual. In addition, this study protocol requires human review of patient-level unstructured data; unstructured data refer to verbatim medical data, including text-based descriptions and visual depictions of medical information, such as medical records, images of physician notes, neurological scans, X-rays, or narrative fields in a database. The reviewer is obligated to report AE with explicit attribution to any Pfizer drug that appear in the reviewed information (defined per the patient population and study period specified in the protocol).

Explicit attribution is not inferred by a temporal relationship between drug administration and an AE, but must be based on a definite statement of causality by a healthcare provider linking drug administration to the AE.

The requirements for reporting safety events on the NIS adverse event monitoring (AEM) Report Form to Pfizer Safety are as follows:

- All serious and non-serious AEs with explicit attribution to any Pfizer drug that appear in the reviewed information must be recorded on the data collection tool (eg, chart abstraction form) and reported, within 24 hours of awareness, to Pfizer Safety using the NIS AEM Report Form.
- Scenarios involving drug exposure, including exposure during pregnancy, exposure during breast feeding, medication error, overdose, misuse, extravasation, lack of efficacy and occupational exposure associated with the use of a Pfizer product must be reported, within 24 hours of awareness, to Pfizer Safety using the NIS AEM Report Form.

For these safety events with an explicit attribution to or associated with use of, respectively, a Pfizer product, the data captured in the medical record will constitute all clinical information known regarding these AEs. These events will be reported by Pfizer to regulators as single case reports, but no follow-up on these related AEs will be conducted.

All HIRD research staff members will complete the Pfizer requirements regarding training on the following: “*Your Reporting Responsibilities: Monitoring the Safety, Performance and Quality of Pfizer Products (Multiple Languages)*” and any relevant Your Reporting Responsibilities supplemental training. This training will be provided to all research staff members prior to study start. All trainings include a “Confirmation of Training Certificate” (for signature by the trainee) as a record of completion of the training, which must be kept in a retrievable format. Copies of all signed training certificates must be provided to Pfizer.

10. PLANS FOR DISSEMINATING AND COMMUNICATING STUDY RESULTS

10.1. Regulatory Authority Reporting

Three (3) annual interim study reports, a final report and a mortality supplement will be submitted to the EMA covering patients in the HIRD who initiate *Duavee* or E+P HRT in 2014-2015, 2015-2016, 2016-2017, and 2017-2018. Each annual report will contain both interim and cumulative data. Reports will each contain 12 months of new post-launch data for *Duavee* as well as all prior data. The first annual report is planned to be submitted to the EMA by 31 March 2016. [Section 4](#) of the protocol contains the planned milestones and submission dates for all annual interim and final study reports.

10.2. Publication

For all peer-reviewed publications relating to this study, Pfizer will follow recognized ethical standards concerning publications and authorship, including Section II - “Ethical Considerations in the Conduct and Reporting of Research” of the Uniform Requirements for

Manuscripts Submitted to Biomedical Journals, <http://www.icmje.org/index.html#authorship>, established by the International Committee of Medical Journal Editors.

10.3. Communication of Issues

In the event of any prohibition or restriction imposed (eg, by clinical hold) by an applicable Competent Authority in any region of the world, or if the investigator is aware of any new information which might influence the evaluation of the benefits and risks of a Pfizer product, Pfizer should be informed immediately.

In addition, the investigator will inform Pfizer immediately of any urgent safety measures taken by the investigator to protect the study patients against any immediate hazard, and of any serious breaches of this NIS protocol that the investigator becomes aware of.

Appendix 1. LIST OF STAND ALONE DOCUMENTS

[Annex 1. Results Table Shells](#)

[Annex 2. ENCePP Protocol Checklist B2311060 Duavive US PASS](#)

Appendix 2. Codes and Algorithms

Candidate codes and algorithms for identification of exposures, endpoints and covariates are provided below. Final definitions will be determined based on further review of the literature in preparation for development of the first Annual Interim Report, and updates may be provided in the event that additional codes become available during the course of the study (e.g., new GPI, ICD-9-CM, HCPCS or CPT codes become available, including introduction of ICD-10 in the US).

Cohort defining medications

Product	GPI Code
Duavee® (Conjugated estrogens/Bazedoxifene)	24995002100330
Activella® (containing Estradiol, Norethindrone)	2499300212x
Angeliq® (containing Drospirenone, Estradiol)	2499300240x
FemHRT® (containing Ethinyl Estradiol, Norethindrone)	2499300225x
Jinteli™ (containing Ethinyl Estradiol, Norethindrone)	2499300225x
Mimvey™ (containing Estradiol, Norethindrone)	2499300212x
Prefest® (containing Estradiol, Norgestimate)	2499300265x
Premphase® (containing Conjugated Estrogens, Medroxyprogesterone)	2499300204x
Prempro® (containing Conjugated Estrogens, Medroxyprogesterone)	2499300204x

Medications included as covariates

Classification	GPI code
Corticosteroids	22x
Lipid lowering agents	39x
Antihypertensives	36x
Antidepressants	58x
Anticonvulsants	72x
Sedatives/ hypnotics	60x
Antimycobacterial agents	90x

Macrolides	35x
Antifungal	11x
Antivirals	12x
Antidiabetics	27x, excluding 2730x and 2757x
Testosterone	23100030x
Local hormone treatments	2600003010x, 2600004000x, 2600004010x 5535001000x, 5535002000x, 5535002010x, 5535002500x, 5535003000x 5537006000x
History of oral contraceptive use	2510x
	2599x
History of intrauterine devise (IUD)	2505x
	2520x

Comorbidities

Description	Diagnosis and Procedure Codes	
	ICD-9-CM	Procedural
Vasomotor symptoms (VMS)	627.2x, 782.62	
Obesity	278.xx, V77.8x	
Polycystic ovarian syndrome (PCOS)	256.4x, 628.xx, 704.1x,	

CVD (i.e. stroke, transient ischemic attack, sudden cardiac death, myocardial infarction, peripheral vascular disease, coronary artery surgery (CABG), or congestive heart failure)
	
093.0x, 394.xx-397.xx, 398.91, 401.9x, 402.xx, 404.01, 404.03, 404.11, 404.13, 404.91, 404.93, 410.xx-414.xx, 424.xx, 425.4x-425.9x, 427.xx, 428.xx, 429.2x, 429.9x, 433.xx-435.xx, 437.3x, 440.xx, 441.xx, 443.1x-443.9x, 447.1x, 557.1x, 557.9x, 798.2x, 798.9x, V43.4x
	
ICD-9-CM procedure: 36.1x, 36.2x, CPT: 33510-33545 33572

Hyperlipidemia
	
272.0x-272.4x
	

Hypertension
	
401.xx-405.xx, 437.2x, V81.1x
	
CPT: 3077F, 3080F

Breast Pain
	
611.71
	

Diabetes
	
250.xx (Type 1: 250.x1, 250.x3; Type 2: 250.x0, 250.x2)
	

Renal Disease	403.01, 403.11, 403.91, 404.02, 404.03, 404.12, 404.13, 404.92, 404.93, 582.xx, 583.0x-583.7x, 585.xx, 586.xx, 588.0x, V42.0x, V45.1x, V56.xx	
Osteoarthritis	715.xx	
Osteoporosis	733.0x, V82.81	
Major Depression	296.2x, 296.3x, 311.xx, V79.0x	HCPCS: G8959, G8960, G8126, G8127, G9193-G9195, CPT: 3088F-3093F
History of VTE/CVA/CHD Event	415.1x, 451.11, 451.19, 451.2x, 451.81, 453.8, 414.xx, 430.xx-438.xx, V12.51-V12.54	
History of Breast, Ovarian, or Endometrial Malignancy	174.xx, 198.81, V10.3x, 198.6x, 183.0x, 236.2x, 182.0x, 198.82, V10.43, V10.42	19120, 58950-58954, 58956-58958, 58960

Family history of cancer	V16.xx	
Hysterectomy	V88.01, V88.02	ICD-9-CM procedure: 68.4x-68.7x CPT: 58150-58294

Potential Algorithms for Claims-Based Identification of Safety Endpoints*

Event	Algorithm
Endometrial Cancer	To be determined via validation
Endometrial Hyperplasia	To be determined via validation
Venous Thromboembolism	Hospitalization with any of the following ICD-9-CM diagnosis codes listed as the principal discharge diagnosis: 415.1x, 451.11, 451.19, 451.2x, 451.81, 453.8x
CHD (i.e. MI, fatal MI, and Sudden Death)	MI defined as a hospitalization with ICD-9-CM code 410.xx (excluding 410.x2) with either (1) a length of stay between 3 and 180 days or (2) discharge status indicating death if length of stay is less than 3 days.
Stroke/TIAs	Hospitalization with ICD-9-CM diagnosis codes 433.x1, 434.x1, 436.x, 437.x1, 437.9x with either (1) a length of stay between 3 and 180 days or (2) death if length of stay is less than 3 days, or hospitalization with a principal discharge diagnosis of 435.xx (TIA)
Breast Cancer	At least two outpatient or one inpatient ICD-9-CM diagnosis code(s) 174.xx.
Ovarian Cancer	At least two outpatient or one inpatient ICD-9-CM diagnosis code(s) 183.0x.

Thyroid Cancer	Thyroidectomy during follow-up and ≥ 2 ICD-9-CM 193.xx diagnosis codes recorded.
Renal Cancer	At least two outpatient or one inpatient ICD-9-CM diagnosis code(s) 189.x
Renal adenoma	At least two outpatient or one inpatient ICD-9-CM diagnosis code(s) 223.x
Gastrointestinal Tract Cancer	At least two outpatient or one inpatient ICD-9-CM diagnosis code(s) 150.x – 159.x
All Cancers (Malignancies)	At least two outpatient or one inpatient ICD-9-CM diagnosis code(s) in the following range: 140.xx-208.xx

*Endpoints will be identified in the NDI based on the presence of applicable codes listed as cause of death.

Algorithms for Claims-Based Identification of Safety Endpoints Identified in the Literature

Event type	Algorithm	Study Population	Validation
CHD (MI, fatal MI and sudden death)	MI defined as a hospitalization with ICD-9-CM code 410.xx (excluding 410.x2) with either (1) a length of stay between 3 and 180 days or (2) death if length of stay is less than 3 days.	HIRD patients receiving COX-2 inhibitors	In HealthCore data, this had a PPV of 88.4% (83.2% - 92.5%), which was higher in patients receiving COX2-inhibitors (92.3 versus 84.2%). Previously reported PPV of 94% in Medicare data.

CHD (MI, fatal MI and sudden death)
	
At least one occurrence of any of the following codes: ICD-9 diagnosis codes: 410 - 414, 433 - 438, 440 - 441, 4439. ICD-9 procedure codes: 3601 - 3609, 361, 362, 3812, 3813, 3818, 3925, 3926, 3929, 3950, 3990 CPT codes: 33510 - 33545, 33572, 34101 - 34111, 34201 - 34203, 35301, 35311 - 35381, 35390, 35454 - 35456, 35459, 35470, 35473 - 35474, 35482 - 35483, 35485, 35492 - 35493, 35495, 35533, 35541 - 35571, 35641, 35646, 35654, 92975, 92980 - 92984, 92995 - 92996
 
*Note - this includes codes for angina, MI, CABG and other procedures not included in the study definition.
	
HIRD patients receiving statins
	
Sensitivity of 96%, specificity of 93% and Kappa of 0.82 (PPV not calculated).

Stroke/TIA
	
An algorithm using primary discharge diagnosis codes for acute ischemic or hemorrhagic stroke (International Classification of Diseases, Ninth Revision, Clinical Modification codes: 430, 431, 433.x1, 434.x1, 436).
	
Medicare patients
	
Positive predictive value of 92.6% (95% confidence interval, 88.8%-96.4%), a specificity of 99.8% (99.6%-99.9%), and a sensitivity of 59.5% (53.8%-65.1%). An algorithm using only acute ischemic stroke codes (433.x1, 434.x1, 436) had a positive predictive value of 91.1% (95% confidence interval, 86.6%-95.5%), a specificity of 99.8% (99.7%-99.9%), and a sensitivity of 58.6% (52.4%-64.7%).

[figure not shown]
Stroke/TIA	Diagnosis codes for acute ischemic or hemorrhagic stroke (International Classification of Diseases, Ninth Revision, Clinical Modification codes: 430, 431, 433.x1, 434.x1, 436) in any position	Medicare data linked to Women's Health Initiative patients	Specificity was 99.7%, negative predictive value was 99.7%, sensitivity was 82.8%, positive predictive value was 85.8%, and $\kappa=0.84$. Whereas specificity and negative predictive value exceeded 99%, sensitivity ranged from 75% to 88% and positive predictive value ranged from 80% to 90% across stroke definitions.
Stroke/TIA	
Ischemic stroke without TIA: (1) Hospitalization with ICD-9-CM diagnosis codes 433.x1, 434.x1, 436.x, 437.x1, 437.9x with either (1) a length of stay between 3 and 180 days or (2) death if length of stay is less than 3 days.
 
(2) Hospitalization with ICD-9-CM diagnosis codes 433.x1, 434.x1 with either (1) a length of stay between 3 and 180 days or (2) death if length of stay is less than 3 days.
	HIRD patients receiving COX-2 inhibitors	
In HealthCore data, algorithm 1 had a PPV of 87.4%, and algorithm 2 95.5% based on review of 175 cases
 
A prior study of Medicare beneficiaries saw a PPV of 96% for algorithm 1.

Breast cancer	
At least one inpatient diagnostic or procedure code for breast cancer: Malignant neoplasm of female breast: 174.0-174.9 Any Incisional breast biopsy: 85.12 Excision or destruction of breast tissue: 85.20 - 85.25 Subcutaneous mastectomy: 85.33-85.36 Mastectomy: 85.41-85.48
	Piedmont cancer registry	The sensitivity of the algorithm was 76.7%, positive predictive value 87.9%.

Breast cancer	At least one claim with ICD-9-CM code 174.xx, 233.0, 238.3 or 239.3.	HealthCore	Not formally validated, however in this study 766 medical records were reviewed to stage breast cancer. Internal communication was that medical records were not excluded based on lack of evidence of breast cancer. 13.4% of cases were stage zero, and 10.3% could not be staged.
Thyroid cancer	Various, see validation	Optum database	PPV of 53.1% (95% CI 42.8 – 63.1) for the ICD-9 code 193 alone. Additionally requiring a thyroidectomy identified 50 of 52 cases but also captured 16 non-cases (PPV 75.8%; 95% CI 63.4-85.1). Requiring a primary inpatient visit with the ICD9 code removed 41 of the 46 non-cases but only identified 16 of the cases (PPV 76.2%; 95% CI 52.5-90.9). One algorithm yielded a PPV of 91.5% (95% CI 78.7-97.2%). This algorithm required cases to have a thyroidectomy during follow-up and ≥ 2 ICD9 193 codes ≤ 90 days of this event, identifying 43 cases and 4 non-cases.
Venous thromboembolism	Multiple	Mini-Sentinel evidence review, various algorithms identified.	The highest PPV (65%-95%) was reported for the combined use of ICD-9 codes 415 (pulmonary embolism), 451, and 453 (deep vein thrombosis) as a VTE event.

*Review of the literature is ongoing; final definitions will be selected using the most current literature and coding available at the start of analyses.

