7.3.4. Covariates

The study will identify and describe the following variables prior to initiation of *Duavee* or comparator E+P HRT treatment. Applicable operational definitions, including International Classification of Diseases, 9th Revision, Clinical Modification (ICD-9-CM) diagnosis, ICD-9-CM procedure, Current Procedural Terminology (CPT) and Healthcare Common

Procedure Coding System (HCPCS) codes used to identify each variable are shown in Appendix 2.

Patient characteristics:

- Age;
- US region of residence;
- Year of cohort entry (ie, index date); and
- Duration of health plan eligibility prior to cohort entry (in months)

Medical conditions diagnosed during the baseline period:

- Vasomotor symptoms;
- Obesity;
- Osteoporosis;
- Cerebrovascular disease;
- Hyperlipidemia;
- Hypertension;
- Breast pain
- Benign breast lumps (fibrocystic nodule)
- Diabetes;
- Renal disease;
- Osteoarthritis;
- Major depression;
- History of CHD
- History of gallbladder disease;
- History of thyroid disease;
- Family history of cancer;

- At least one diagnosis code indicative of a prior safety event of interest (exclusive of cancers as this is a baseline exclusion criterion).

Use of prescription medications during the baseline period prior to the start of *Duavee* or E+P HRT:

- Corticosteroids;
- Lipid lowering agents;
- Antihypertensives;
- Antidepressants;
- Sedatives/hypnotics;
- Anticonvulsants;
- Antimycobacterials;
- Macrolides;
- Antifungals;
- Antivirals;
- Antidiabetics;
- History of oral contraceptive use;
- History of intrauterine device (IUD) exposure; and
- Unopposed estrogen HRT
- Selective estrogen receptor modulators (SERMs)
- Testosterone
- Local hormone treatments

Additionally, the analyses will describe the most frequently occurring diagnoses and medications seen during the baseline period, the reasons that follow-up was censored and characteristics of medication use during the follow-up period, specifically duration of therapy and time since most recent exposure (measured at the time of censoring from study).

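### Two candidate cardiovascular covariate lists in Appendix 2 do not match their labels or Section 7.3.4: the CVD row counts unspecified hypertension, and the prior-event row omits the MI code 410.xx

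*Protocol*

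**What the plan says.** Protocol Section 7.3.4 lists the baseline variables and refers to Appendix 2 for their codes. Among them are cerebrovascular disease, hypertension, history of CHD, and a catch-all for earlier endpoint events: "At least one diagnosis code indicative of a prior safety event of interest", cancers excepted.

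Four entries in Appendix 2 bear on these:

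- **CVD row, description:** "CVD (i.e. stroke, transient ischemic attack, sudden cardiac death, myocardial infarction, peripheral vascular disease, coronary artery surgery (CABG), or congestive heart failure". Hypertension is not named.
- **CVD row, codes:** the list includes "398.91, 401.9x, 402.xx, 404.01" and, further on, "410.xx-414.xx, 424.xx, 425.4x-425.9x, 427.xx, 428.xx".
- **Hypertension row, codes:** "401.xx-405.xx, 437.2x, V81.1x".
- **History of VTE/CVA/CHD Event row, codes:** "415.1x, 451.11, 451.19, 451.2x, 451.81, 453.8, 414.xx, 430.xx-438.xx, V12.51-V12.54".

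The endpoint table in the same appendix identifies the non-fatal part of the CHD endpoint by 410.xx: "MI defined as a hospitalization with ICD-9-CM code 410.xx (excluding 410.x2". Appendix 2 calls all its codes candidates and says that final definitions will be settled in preparation for the first interim report.

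**The concern.** Each row should measure what its label says, and together the rows should deliver the Section 7.3.4 covariates. Two do not. The CVD row takes in a hypertension code outside its own description. The history row, the only Appendix 2 row with CHD history in its title, leaves out the code of the CHD endpoint.

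This matters because women with a prior MI stay in the cohort. Section 7.2.2 does not exclude them, and Patient B in Figure 3 of Section 7.4 has an MI at baseline. Under Section 7.7.1, the Section 7.3.4 variables are compared between cohorts to find the confounders that matching must address. Section 7.9 warns of channelling and concedes that smoking and BMI are unavailable, so coded cardiovascular history is one of the few controls left for the CHD, stroke and mortality hazard ratios. If the flag that carries prior MI mostly records hypertension, a balance table can look satisfactory while prior MI differs between groups.

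**Working it through.** The plan states no figure on this point. The check is a membership test of the printed code ranges, followed by an illustration on assumed prevalences.

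**Step 1. Which row contains which code** (all from Appendix 2)

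| ICD-9-CM code | CVD row | History row | Hypertension row |
|---|---|---|---|
| 401.9 | yes | no | yes |
| 410 | yes | no | no |
| 411, 412, 413 | yes | no | no |
| 414 | yes | yes | no |
| 433 to 435 | yes | yes | no |
| 430, 431, 436, 437.9, 438 | no | yes | no |

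**Step 2. What the three flags show for a given woman**

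| Baseline codes | CVD | History | Hypertension |
|---|---|---|---|
| 401.9 only | 1 | 0 | 1 |
| 401.9 and 410 | 1 | 0 | 1 |
| 410 only | 1 | 0 | 0 |
| none of these | 0 | 0 | 0 |

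The first two lines are identical. A woman coded 401.9x has the same three flags with or without an MI coded 410.xx, unless she also has a code in the history row such as 414.xx. In the third line the MI does show, although mixed with every other condition in the CVD row.

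**Step 3. Illustration of dilution.** The documents give no prevalences. Assume, independently of each other:

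- h = share coded 401.9x, 20% to 40%
- m = share with a prior MI, 0.2% to 1%
- o = share with any other code in the CVD row, 3% to 8%

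Flag prevalence with 401.9x = 1 − (1 − h)(1 − m)(1 − o); without it = 1 − (1 − m)(1 − o). The share of flagged women with a prior MI is m divided by the flag prevalence.

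Worked case, h = 0.30, m = 0.005, o = 0.03:

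- With 401.9x: 1 − 0.70 × 0.995 × 0.97 = 0.324; MI share 0.005 / 0.324 = 1.5%.
- Without: 1 − 0.995 × 0.97 = 0.035; MI share 0.005 / 0.03485 = 14%.

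Over the assumed ranges:

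| | Flag prevalence | MI share of flagged women |
|---|---|---|
| 401.9x in the CVD row | 23% to 45% | 0.4% to 4% |
| 401.9x removed | 3% to 9% | 2% to 25% |

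These figures describe the purity of a flag, not bias in a hazard ratio. They also show that removing 401.9x sharpens the CVD flag without isolating MI. That needs a CHD-history covariate containing 410.xx.

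**The case against.** A reader might infer that prior MI cannot be balanced at all. The documents do not support that: the CVD row contains 410.xx to 414.xx, so a baseline MI enters the propensity score. Nor is MI always confused with hypertension. The separate Hypertension flag contains 401.9x, so a woman positive on CVD and negative on Hypertension has no 401.9x, and boosted regression can use the two flags jointly. The ambiguity is confined to women coded 401.9x.

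A reader might also infer that prior stroke is lost. It is not: the history row covers 430.xx to 438.xx. The stroke comparison is affected only through prior MI. Nor is the score the sole control, since Section 7.7.3 also plans doubly robust estimation and speaks of using the full diagnostic and procedural information in the HIRD. That estimation still depends on how the covariates are coded, however, and the protocol commits to no separate MI variable.

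The strongest objection is that the lists are provisional and that final covariate codes are often left to the SAP, which is not at hand. Several other Section 7.3.4 covariates, such as gallbladder and thyroid disease, have no row either, so Appendix 2 is not exhaustive. This lowers the weight of the point but does not remove it. A row that contradicts its own label, and a prior-event row lacking the endpoint's code, are errors in what is printed. The stated route to final definitions, literature review and newly available codes, is not aimed at such mismatches.

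The effect may also be small. Suppose prior MI were 1% in one group and 0.2% in the other with no control by any flag. An assumed risk ratio of 5 for the endpoint gives a bias factor of (1 + 0.01 × 4) / (1 + 0.002 × 4) = 1.04 / 1.008 = 1.03; a risk ratio of 10 gives 1.09 / 1.018 = 1.07. These inputs are not in the documents, so the figures are an example rather than a bound.

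**Conclusion.** Both coding errors stand on the printed lists alone and need no assumption. The CVD row includes unspecified hypertension, which it does not describe and which is counted elsewhere. The history row omits 410.xx and so does not deliver the CHD-history and prior-safety-event covariates of Section 7.3.4.

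The consequence is limited. No printed covariate isolates prior MI, and the flag that captures it is constant among women coded 401.9x, so balance on that flag does not assure balance on prior MI. The comparisons concerned are secondary. It would go too far to conclude that their hazard ratios are biased: the size and direction of any bias are unknown, and the dilution figures rest on assumed, independent prevalences. This is a correctable specification error and does not touch the endometrial primary endpoints.

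**What to change.** Before the code lists are finalised for the first interim report:

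1. Delete 401.9x from the CVD row. The Hypertension row already counts it. 402.xx and the listed 404 codes overlap that row too; a line saying whether they are intended would settle the matter.
2. Add 410.xx and old MI (412) to the history row.
3. Provide a CHD-history covariate that includes MI, and a cerebrovascular covariate, as Section 7.3.4 lists them. Use both in the propensity model and the balance table.

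Separating VTE history is optional, since Section 7.3.4 lists no separate VTE covariate. Adding 411.xx and 413.xx is also optional, because Section 7.3.2 defines the CHD endpoint as MI and sudden death.

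The cost is a code-list edit and two more precisely defined covariates. The data are already in the HIRD, so no new collection is needed.

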7.7.1. Main Analyses

The analyses will describe patients that initiate *Duavee* and the comparator E+P HRT cohort with respect to demographic and clinical characteristics as enumerated in [Section 7.3.4](#). Reasons for censoring will also be described by exposure group. Descriptive comparisons of the two cohorts will be done to document their differences at baseline and to identify potential confounders to be addressed in the propensity matching.

For each of the primary endpoints (i.e., endometrial hyperplasia and endometrial cancer), an IR will be calculated as the number of women meeting a claims-based algorithm for each outcome (first event only) divided by person-time at risk.

The IR and its associated 95% CI will be presented for each cohort overall and stratified by categorical patient age at cohort entry, total duration of *Duavee* or E+P HRT treatment (long vs. short), time since last exposure to *Duavee* or E+P HRT, exposure to local hormone therapy (See Appendix 2), and by presence (Y/N) of an osteoporosis diagnosis within the 90 days before or after initiation of *Duavee* or E+P HRT. Duration of treatment and time since last exposure will be categorized based on observed data distributions. The feasibility of these stratifications and of a possible analysis that stratifies simultaneously by duration of treatment and time since last exposure will be determined based on the number of observed safety events.

Further details of the validation process are described in Appendix 3 and will be contained in the separate Endpoint Algorithm Development Report.

Hazard ratios will be estimated that represent the relative risk associated with initiating *Duavee* as compared to E+P HRT. It is planned to conduct both crude (unadjusted) and adjusted analyses to assess the HR for each of the primary endpoints. Adjusted analyses will use propensity score matching to ensure comparability between treatment groups. Further discussion of the methods to be used in computing propensity scores is included in [Section 7.7.3](#).

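### Four Appendix 2 disease rows include screening codes, so women who were only screened count as having obesity, hypertension, osteoporosis or major depression

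*Protocol*

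**What the plan says.** Section 7.3.4 of the protocol lists obesity, osteoporosis, hypertension and major depression under the label "Medical conditions diagnosed during the baseline period" and sends the reader to Appendix 2 for the operational definitions.

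The comorbidity table in Appendix 2 gives these diagnosis codes:

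- Osteoporosis: "733.0x, V82.81"
- Hypertension: "401.xx-405.xx, 437.2x, V81.1x"
- Major depression: "296.2x, 296.3x, 311.xx, V79.0x"
- Obesity: 278.xx together with V77.8x

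No row says that the V-code counts only when a disease code is also present.

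Section 7.7.1 plans to present the incidence rates of the two primary endpoints by several stratifiers. One of them is the "presence (Y/N) of an osteoporosis diagnosis within the 90 days before or after initiation of" study treatment. That section names no separate code list for osteoporosis.

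Appendix 2 treats its lists as provisional: "Final definitions will be determined based on further review of the literature in preparation for development of the first Annual Interim Report".

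**The concern.** A screening code shows that a test was done. It does not show what the test found. With the rows as printed, a woman whose bone-density scan was normal is recorded as having osteoporosis. The same happens to a woman screened for obesity, high blood pressure or depression with a negative result.

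Two uses of these variables are exposed.

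1. **Propensity score.** The four conditions are among the baseline covariates from which confounders are to be identified. Obesity matters most. Section 7.9 concedes that body mass index cannot be obtained from the claims and names it as a source of residual confounding, so the claims-based flag is the only obesity measure among the listed covariates. Mixing screened women into it weakens adjustment where the protocol already admits weakness.
2. **Osteoporosis stratum.** If the Appendix 2 row defines it, its Yes category mixes women with the disease and women who were only tested, and the reported rate does not describe the group named in the label.

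**Working it through.** **What the codes mean.** In ICD-9-CM, V82.81, V77.8, V81.1 and V79.0 are special-screening codes for osteoporosis, obesity, hypertension and depression. The protocol does not print these meanings; they belong to the coding standard it adopts in Section 7.3.4. The protocol itself uses V-codes elsewhere for things other than current disease: V88.01 for post-hysterectomy status (Section 7.1) and V16.xx for family history of cancer (Appendix 2).

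**The texts side by side.** Section 7.3.4 says the conditions are diagnosed, and Section 7.7.1 speaks of a diagnosis. The four rows accept a code that is not a diagnosis. The conflict is in the wording and needs no arithmetic.

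**How much of the osteoporosis stratum could be screen-only.** The protocol states no figure on this point, so there is none to reproduce. Both inputs are assumptions:

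- d = share of initiators with a 733.0x code in the window, assumed 3% to 15%
- s = share of the remaining women who carry V82.81 in the window, assumed 1% to 30%

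Women with both codes count as diseased, so overlap is handled. The screen-only share of the Yes stratum is

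f = s(1 − d) / [d + s(1 − d)]

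| d | s = 1% | s = 5% | s = 10% | s = 30% | s at which f = 50%, d/(1 − d) |
|---|---|---|---|---|---|
| 3% | 24% | 62% | 76% | 91% | 3.1% |
| 5% | 16% | 49% | 66% | 85% | 5.3% |
| 10% | 8% | 31% | 47% | 73% | 11.1% |
| 15% | 5% | 22% | 36% | 63% | 17.6% |

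Lowest cell: 0.01 × 0.85 / (0.15 + 0.01 × 0.85) = 0.0085 / 0.1585 = 5%. Highest cell: 0.30 × 0.97 / (0.03 + 0.30 × 0.97) = 0.291 / 0.321 = 91%. The share passes from minority to majority within the assumed ranges. With V82.81 removed it is 0% by construction.

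**What contamination does to the stratum rate.** Assume that screen-only women have the same event rate as women without osteoporosis, and take f as a share of person-time. If the true rate ratio (osteoporosis versus none) is RR, the observed ratio is (1 − f)RR + f.

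| True RR | f = 10% | f = 25% | f = 50% | f = 75% |
|---|---|---|---|---|
| 0.5 | 0.55 | 0.625 | 0.75 | 0.875 |
| 2.0 | 1.90 | 1.75 | 1.50 | 1.25 |

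Under that assumption the stratum rate always moves toward the rate of women without osteoporosis; how far depends on f.

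**Propensity-score covariates.** The documents give no frequencies for the obesity, hypertension or depression codes and no covariate effects, so the residual confounding cannot be sized from them.

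**The case against.** A reader might infer that the osteoporosis stratum would consist mostly of women who were only screened. The documents do not support that. It requires screen-only women to outnumber women with 733.0x, the protocol gives neither frequency, and the 5% to 91% range covers both outcomes.

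Other objections carry some weight:

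- **The link to the stratum is inferred.** The sentence in Section 7.7.1 points to Appendix 2 for local hormone therapy but not for osteoporosis. The stratum's window also runs past initiation, so it is not the baseline covariate of Section 7.3.4. This stands: the stratum part of the point is conditional. No other osteoporosis definition is given, however.
- **The lists are provisional.** This lowers the severity. It does not make a screening code consistent with a diagnosis, and the stated route to finalisation is a literature review, with updates foreseen for additional codes. Neither is aimed at removing codes of this kind.
- **The output is narrow.** In Section 7.7.1 the osteoporosis split applies to incidence rates, and Section 7.7.6.2 leaves it out of its own list of stratifiers. Whether it appears at all depends on event counts: "The feasibility of these stratifications and of a possible analysis that stratifies simultaneously by duration of treatment and time since last exposure" is to be judged from the events observed. This stands for the stratum. The covariate use carries no such condition.
- **Other covariates help.** Antihypertensives and antidepressants are separate covariates, and Section 7.7.3 draws broadly on prescriptions, diagnoses and procedures. This softens the effect for treated hypertension and depression. The covariate list has no comparable medication class for obesity.
- **A 733.0x stratum would not isolate prevention users.** Osteoporosis prevention is part of the US indication (Section 5), and women treated for prevention need not have the diagnosis. This is correct. The change makes the label true; it does not create a stratum of prevention users.

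**Conclusion.** The point holds as a conflict within the protocol: four disease rows admit women who were only screened, while Section 7.3.4 describes diagnosed conditions. This rests on the printed code lists and on the standard ICD-9-CM meaning of the four codes.

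The consequence is added misclassification in four propensity-score covariates, of most concern for obesity. The size cannot be stated from the documents. If the Appendix 2 row also defines the osteoporosis stratum, that stratum is contaminated to an unknown extent. Its rate would be pulled toward that of women without osteoporosis, provided that screen-only women share their risk.

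A reader might also infer that the primary hazard ratios are directly distorted. They are not stratified by osteoporosis and are touched only through the propensity score. The correction is worth making because it is nearly free and the lists are still open. The point does not threaten the main comparison.

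**What to change.** - In Appendix 2, delete V77.8x, V81.1x, V82.81 and V79.0x from the obesity, hypertension, osteoporosis and major depression rows.
- If screening is wanted as a marker of preventive-care use, carry the four codes as a separate baseline preventive-screening covariate in the propensity score.
- In Section 7.7.1, state that the osteoporosis stratum is defined by 733.0x only.

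The cost is four code deletions and one added sentence. The drawback is a smaller osteoporosis Yes stratum, which makes it less likely that event counts will allow that split to be shown.
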